10.0 PREMATURE DISCONTINUATION FROM STUDY

A subject may be involuntarily discontinued from the study for the following reasons, at the discretion of the investigator and the Sponsor:

- Noncompliance with study procedures and visits to the investigational site
- Significant safety event that does not resolve within 7 days of lowering the dose or other clinical interventions.
- Lost to follow-up after every attempt has been made to contact the subject including sending a registered letter.
- Subject withdraws consent.

The reason for the discontinuation should be recorded.

The Principal Investigator and the Institutional Review Board/Ethics Committee (IRB/EC) reserve the right to prematurely terminate the study in the interest of subject safety and welfare. The Sponsor reserves the right to prematurely terminate the study at any time for administrative reasons. If subjects are discontinued, they will be titrated off of hydromorphone hydrochloride therapy and placed on other alternative treatments at the discretion of the investigator and according to standard medical practice and manufacturer instructions for the intrathecal pump.

11.0 PREMATURE DISCONTINUATION FROM STUDY DRUG

The Investigator will continue to monitor subjects who have discontinued prematurely from study drug due to an AE (serious and non-serious) until resolution or stabilization of the AE.

The Investigator (or designee) must complete all applicable CRF pages for subjects who discontinue study drug prematurely. Final visit procedures (See Appendix A) should be conducted for any subject who discontinues study drug prematurely.

Subjects who prematurely discontinue study drug for any reason other than toxicity may be reentered into the study after consultation between the Investigator and the Sponsor or the Sponsor's designee. Dosing of a subject who previously discontinued in the study is at the discretion of the Sponsor. However, subjects who drop out due to toxicity will not be replaced.

12.0 PRODUCT SPECIFICATIONS

12.1 Description

Hydromorphone hydrochloride for injection (intrathecal) 2 mg/mL and 10 mg/mL is provided in single use vials of 40,000 mcg per 20 mL (2,000 mcg/mL) or 200,000 mcg per 20 mL (10,000 mcg/mL) for intrathecal administration only.

The drug product is manufactured under current Good Manufacturing Practices (cGMP) at DSM Pharmaceuticals, Inc, or at Patheon Manufacturing Services LLC, contract manufacturing facilities that have undergone FDA inspection.

12.2 Formulation, Packaging, and Labeling

Hydromorphone hydrochloride for injection (intrathecal) 2 mg/mL and 10 mg/mL will be supplied in single use vials and contains hydromorphone hydrochloride and water. Vials will be packaged in boxes for shipment to the clinical sites.

Study drug vial will be affixed with a single label panel containing the following information:

Hydromorphone Hydrochloride Injection (Intrathecal) 40,000 mcg/20 mL (2,000 mcg/mL) or 200,000 mcg/20 mL (10,000 mcg/mL)

Lot Number: XXXXXX

Manufacturing Date: MM-DD-YYYY Store at Room Temperature (15 to 30°C)

Protect from light - store in package until ready to use

Caution: New Drug – Limited by U.S. Federal Law to Investigational Use Manufactured for CNS Therapeutics, Inc.

12.3 Receipt, Storage and Stability of Hydromorphone Intrathecal

Hydromorphone hydrochloride for injection (intrathecal) 2 mg/mL and 10 mg/mL vials will be packaged in boxes for shipment to investigational sites. During shipment excursions are permitted to 4° to 30°C (39° to 86°F), and after receipt drug should be stored at 15° to 30°C (59° to 86°F) until use. Excursions from the temperature storage condition should be reported to the study monitor.

12.4 Preparation and Administration of Study Drug

There is no manipulation or preparation of study drug other than filling into the intrathecal programmable infusion pump according to the manufacturer's instructions.

12.5 Ordering and Distribution of Study Drug

Study drug may be requested by submission of a medication request form. The form may be submitted to the Sponsor or designee by facsimile or electronic mail PDF as per the instructions on the drug ordering form.

12.6 Accountability of Study Drugs

All study drugs received, dispensed, and returned must be accounted for in the study drug Dispensing Log, including:

- Subject number and initials.
- Date study drug was dispensed.
- Quantity dispensed.
- Quantity returned.
- Amount wasted (if applicable).

All study drug received and dispensed by the Investigator will be inventoried and accounted for throughout the study. The study drug must be stored in a restricted area with limited access. Contents of the study drug containers must not be combined.

The Investigator must maintain an accurate, up to date Dispensing Log for all study drugs supplied by the Sponsor. The study drug Dispensing Log and remaining drug inventory will be reviewed at each monitoring visit by the Sponsor-designated clinical monitor.

Study drug dispensed for all subjects must be recorded on subject specific Drug Accountability Log.

The study drug supplied for this study is for use only in subjects properly consented and enrolled into this protocol. Study drugs must be kept in a secure location physically separated from standard clinic or office drug supplies.

13.0 SAFETY MONITORING AND ADVERSE EVENTS

13.1 Adverse Events

Data regarding treatment-emergent AEs will be collected in this study. Treatment-emergent AEs are events that are not present at baseline, or if present at baseline, have worsened in severity.

The descriptions and grading scales found in the Common Terminology Criteria for Adverse Events (CTCAE) v 4.03 will be used for AE reporting. A copy of the CTCAE v 4.03 is provided in Appendix B.

The medical monitor and contact information for this study are presented below:

[name], MD	Medical Director, Social & Scientific	Office: [contact] [contact]	E-mail: [contact]
	Systems, Inc. [name] 20910		

Definition of Adverse Events and Adverse Drug Reactions:

Adverse events in the CRF will be classified according to the most recent FDA definitions and in a manner consistent with ICH guidelines. As such the following definitions will be used:

An adverse event (AE) is any unfavorable and unintended sign, symptom, or disease temporally associated with the use of an investigational (medicinal) product (IP) or other protocol-imposed intervention, regardless of attribution. An AE may include intercurrent illnesses or injuries that represent an exacerbation (increase in frequency, severity, or specificity) of pre-existing conditions (worsening of asthma). A laboratory abnormality will be reported on the "Adverse Event" case report form only if it is associated with clinical sequelae or requires therapeutic intervention. Whenever possible, it is preferable to record a diagnosis as the AE term rather than a series of symptoms relating to a diagnosis. AEs will be graded according to the NCI Common Terminology Criteria for Adverse Events (CTCAE) v 4.03.

The reporting period for AEs starts after the first administration of study drug on Day 1 and ends after discontinuation of study medication.

SAEs must be followed until resolution by the PI, even if this extends beyond the study-reporting period. Resolution is defined as the return to baseline status or stabilization of the condition with the expectation that it will remain chronic.

The investigator will assess AEs for severity, for relationship to Investigational Product (IP), and as to whether the event meets one or more of the definitions of an SAE. The investigator will determine the relationship of an AE to the IP and will record it on the source documents and AE CRF, using the categories defined below.

Table 13–1 Causality Categories for AE Descriptions

Causality Category	Description
Unlikely	A clinical event, including laboratory test abnormality, with a temporal relationship to drug administration which makes a causal relationship improbable, and in which other drugs, chemicals or underlying disease provide plausible explanations. For the purpose of this protocol, the term unlikely will be considered not related to study medication and an "Adverse Event".
Possible	A clinical event, including laboratory test abnormality, with a reasonable time sequence to administrations of the drug, but which could also be explained by concurrent disease or other drugs or chemicals. Information on drug withdrawal may be lacking or unclear. For the purpose of this protocol an event that has possible relationship to study medication will be defined as a "Suspected Adverse Drug Reaction".
Probable	A clinical event, including laboratory test abnormality, with a reasonable time sequence to administration of the drug, unlikely to be attributed to concurrent disease or other drugs or chemicals, and which follows a clinically reasonable response on withdrawal. For the purpose of this protocol an event that has probable relationship to study medication will be defined as a "Adverse Drug Reaction".

Whenever possible, it is preferable to record a diagnosis as the AE term rather than a series of symptoms relating to a diagnosis. AEs will be graded according to the NCI Common Terminology Criteria for Adverse Events (CTCAE) v4.03. The investigator will determine the severity of each AE based on CTCAE criteria and will record the grade of the event on the source documents and AE CRF.

01 August 2016 44 CONFIDENTIAL

In order to classify adverse events and diseases, preferred terms will be assigned by the sponsor or its designee to the original terms entered on the CRF, using MedDRA. CTCAE is provided in Appendix B.

Table 13–2: Severity Assessment Terminology for Reporting Adverse Events (CTCAE v4.03)

CTCAE Grade	Common Term	Description
1	Mild	Mild; asymptomatic or mild symptoms; clinical or diagnostic observations only; intervention not indicated.
2	Moderate	Moderate; minimal, local or noninvasive intervention indicated; limiting age-appropriate instrumental Activities of Daily Living (ADL).
3	Severe	Severe or medically significant but not immediately life- threatening; hospitalization or prolongation of hospitalization indicated; disabling; limiting self care Activities of Daily Living (ADL).
4	Life- Threatening	Life-threatening consequences; urgent intervention indicated.
5	Death	Outcome of AE was death

For those AEs that are not described on the CTCAE v4.03, such AEs will be graded according to the same scale as defined above.

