3.0 STUDY DESIGN

3.1 Description of Trial Design

This is an open-label, single-arm study to evaluate the safety of hydromorphone hydrochloride given by continuous intrathecal infusion using an implantable pump device. This clinical trial will be conducted at up to 30 clinical trial sites that are experienced with the use of intrathecal opioids. This study will enroll both subjects on a current opioid (eg, morphine or hydromorphone hydrochloride) intrathecal medication as well as naïve subjects not currently on intrathecal opioid medications. Dosing regimens allowed in this study will include simple continuous, complex continuous and Personal Therapy Manager (PTM) dosing.

For subjects entering the trial already on a therapeutic dose of another intrathecal hydromorphone hydrochloride, the hydromorphone hydrochloride will be replaced by the study

drug (hydromorphone hydrochloride for intrathecal injection) on a 1:1 basis without dose adjustment or optional titration days. The subject is considered at a therapeutic dose and will start the study on Day 1.

Subjects converted from an intrathecal opioid therapy other than hydromorphone hydrochloride to the study drug will be dosed with the study drug according to the following conversion scheme:

Subject on Morphine or on another Opioid ³	Conversion Ratio
Dose ≤ 30 mg IT morphine and tolerating therapy well	1:61
Dose > 30 mg IT morphine or subject has significant side effects on morphine	1:12 ²

¹Conversion is based on mg-morphine equivalence such that for each 6 mg morphine sulfate the dose is converted to 1 mg hydromorphone hydrochloride.

Subjects who are converted directly to the study drug based on the 1:6 morphine-equivalence ratio are, by definition, at a therapeutic dose and must start the study on Day 1 without titration. Dose adjustments may be performed at subsequent visits, based on the investigator discretion.

For subjects using 1:12 conversion ratio, due to safety considerations, the conversion will be followed by up to five (5) optional titration days (Titration Days A, B, C, D and E) to achieve a therapeutic dose that is well tolerated before starting Day 1. These optional titration days may be three (3) to fourteen (14) days apart.

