Subjects who are naïve to intrathecal analgesics will have the pumps filled initially with a 2 mg/mL hydromorphone hydrochloride for intrathecal injection. Naïve subjects will be initiated on a dose between 0.1 mg/day and 0.5 mg/day, based on their current opioid dose and the discretion of the investigator. These subjects will be allowed up to five (5) optional titration days to achieve a therapeutic dose of hydromorphone prior to starting the long term safety period on Day 1 of this study. These optional titration days may be three (3) to fourteen (14) days apart. It is suggested that prior to a dose adjustment above 1 mg/day, the pump should be drained and refilled with 10 mg/mL hydromorphone hydrochloride undiluted and pump speed adjusted to achieve the target dose. Dose adjustments may continue as needed to optimize the therapy. After achieving a therapeutic dose of hydromorphone hydrochloride, additional intrathecal concomitant medications may be added to the therapy to optimize pain control for these subjects (see Section 3.6.2).

Subjects continuing on therapy from the CNS-HYD201US trial may remain at their current dose of hydromorphone hydrochloride or may have a dose adjustment if clinically indicated, beginning at Day 1 of this study. Subjects who were titrated off of hydromorphone hydrochloride as part of the CNS-HYD201US control arm will be titrated back to a therapeutic dose using one or more optional titration days prior to Day 1 of this study.

A maximum dose 10 mg/day intrathecal hydromorphone hydrochloride is permitted at any time during this study. For subjects on PTM dosing regimens, the maximum daily dose will include the combined continuous dose and the allowed maximum PTM dose. All subjects should be contacted by telephone 24 hours after initiating study medication of hydromorphone hydrochloride.

Subjects may be given FDA approved oral supplemental opioid medication and other FDA approved non-opioid medications to help manage pain during the 12 month treatment.

Subjects will remain on therapy for a total of 12 months or until discontinuation from the study. During this continuous dosing period, dose adjustments (up or down) are permitted to manage pain or side effects provided the maximum 10 mg/day dose of hydromorphone hydrochloride is

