5.0 SAFETY ASSESSMENTS

5.1 Collection of Adverse Events Data

Data regarding treatment-emergent AEs will be collected in this study. Treatment-emergent AEs are events that are not present at baseline, or if present at baseline, have worsened in severity. AEs will be assessed at each study visit from the time of study drug administration, during optional titration days, and for the long-term safety period starting on Study Day 1 through the final visit. AEs assessed by the Investigator as related to study drug and "ongoing" at the final scheduled study visit will be monitored by the Investigator until resolved or stabilized.

Protocol CNS-HYD202US

Version: 7.0

Each subject will be observed and queried by the Investigator or his/her designee at each study visit for any continuing AEs or new AEs since the previous visit. If an AE occurs between study visits, regardless of causal relationship to study drug and in the opinion of the Investigator, requires a study visit for full evaluation, the subject will be asked to return to the site for an unscheduled visit.

Any AE reported by the subject or noted by the Investigator or his/her designee will be recorded. The following information will be recorded for each AE: description of the event, date and time of onset, date and time of resolution, severity, causal relationship to study drug, outcome, action taken with the study drug and any treatment given.

All abnormal changes from baseline in physical examination findings including vital signs will be collected, graded with regards to severity or clinical significance, assessed for causal relationship, and will be recorded.

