13.2.1 Reporting Requirements for Serious Adverse Events

Initial Reporting

SAEs (based on FDA/ICH definition of an SAE) require immediate reporting to Mallinckrodt or designated representative.

For all fatal or life-threatening events, the investigator(s) or designee must report information within 24 hours to the Medical Monitor at [contact].

For all SAEs, the investigator(s) or designee must complete the SAE report form with the minimum information required by FDA and ICH and fax it to Mallinckrodt Pharmacovigilance at [contact] within 24 hours of first knowledge of the event even if the experience does not appear to be related to the study drug.

The investigator(s) or designee will receive acknowledgement of receipt of the SAE report form from Mallinckrodt.

Should the investigator(s) or designee have any difficulty in sending the SAE report, they may contact Mallinckrodt Pharmacovigilance at [name] (24 hour call center) or email: [contact].

If there is any doubt about whether the information constitutes an SAE, the information is to be treated as an SAE.

Follow Up Reporting

The investigator(s) or designee must complete an SAE report form for all follow-up information received and fax it to the sponsor [contact] within 24 hours of receipt of additional or updated information (eg, detailed written descriptions that include copies of relevant subject records, autopsy reports and other supporting documents). The investigator(s) or designee will receive acknowledgement of receipt for each SAE report form from Mallinckrodt.

The investigator(s) or designee is required to report immediately unexpected SAEs to the responsible IRB/IEC.

01 August 2016 46 CONFIDENTIAL

All adverse events (serious and non-serious) occurring in subjects from the time of informed consent through the completion of the follow-up telephone call will be documented as an AE in the source and in the eCRF. All fields on the AE eCRF page should be completed for each event with a full description of the event and date and time of onset and resolution. The investigator must follow up on all AEs and SAEs until the events have subsided, until values return to within the acceptable range, the investigator determines that follow-up is no longer necessary, or the subject is referred to a nonstudy physician.

The sponsor will report SAEs to the FDA and investigators according to local regulations.

Table 13-3 Reporting Requirements for Adverse Events

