Appendix A: Schedule of Study Procedures									

Table A-1: Schedule of Study Procedures

Study Procedure					Visit Schedule								
Study Day ^a	Screening Days -14 to 1 ^b	Baseline Days -3 to 1 ^b	Baseline for HYD201US Subjects ^b	Optional Titration Days ^{b,c}	Day 1 ^{b,d}	Day 28	Day 56	Day 80	Day 104	Day 160	Day 216	Day 286	Final Study Visit Day 365
Signed Informed Consent	X ^e		X										
Medical History ^f	X		*										
Complete physical exam ^g	X		*										X
Vital signs and Weight ^g	X	X	*	X	X	X	X	X	X	X	X	X	X
Urine pregnancy test ^g	X	X	X										X
ECG ^g	X		X										
CBC, CMP, Urinalysis ^g	X		X										
Concomitant medication assessment	X	X	*	X	X	X	X	X	X	X	X	X	X
Adverse event assessment	X	X	*	X	X	X	X	X	X	X	X	X	X
Hydromorphone Hydrochloride Pump Dose Adjustment and Refills h,I,l			X	X	X	X	X	X	X	X	X	X	X^{l}
Oral Opioid			X										·
Clinical evaluation for Granulomas ^j	X		*		X	X	X	X	X	X	X	X	X
VASPI Assessment ^k	X	X	*	X	X	X	X	X	X	X	X	X	X
COWS Assessment ^k		X	*	X									X
BPI^k		X	*			X		X		X		X	X
PGIC ^k		X	*			X		X		X		X	X

- a. Study Day is based on Day 1 defined as the first day a subject achieves a therapeutic dose of hydromorphone therapy. There is no Day 0 in this trial. Optional titration days for subjects below therapeutic levels will not be counted towards the 365 day study period. All visit days are +/- 7 days during the long-term extension phase of the study. Additional unscheduled visits may be scheduled to make dose adjustments or prescribe oral medication to manage pain and withdrawal symptoms as deemed appropriate by the investigator.
- b. Screening period is 14 days. Screening, Baseline and/or Initiation of Dosing (ie, Optional Titration Day or Day 1) visits may be combined. For subjects entering the CNS-HYD202US clinical trial that are transitioning from the CNS-HYD201US efficacy trial, these subjects will not be required to repeat Screening. For these subjects the last day of the CNS-HYD201US trial will be considered the first day (either optional titration day or Day 1) of the CNS-HYD202US trial. Baseline assessments will be completed as part of the final day (Day 119 or Treatment Failure day) and only additional activities or tests shown on the Schedule of Events (shown in table of events as "X") for these subjects are required to enter the CNS-HYD202US trial. Tests that are done as part of the final visit of the CNS-HYD201US trial and will not be repeated in this study are shown in the table with a "*".

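### Protocol 5.1, 13.1 and 13.2.1 give three different AE windows for the primary endpoint, and 13.1 as written leaves out on-drug titration before Day 1

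*Protocol*

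**What the plan says.** AEs and SAEs are the primary endpoint (Protocol 3.2.1; SAP 7.1). Three protocol sections say when they are collected.

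- **Protocol 13.1:** "The reporting period for AEs starts after the first administration of study drug on Day 1 and ends after discontinuation of study medication".
- **Protocol 5.1:** "AEs will be assessed at each study visit from the time of study drug administration, during optional titration days", and then through the long-term period to the final visit.
- **Protocol 13.2.1:** all events, serious or not, "from the time of informed consent through the completion of the follow-up telephone call will be documented as an AE".

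Appendix A, footnote a, fixes what Day 1 means: "Study Day is based on Day 1 defined as the first day a subject achieves a therapeutic dose of hydromorphone therapy". The same footnote adds: "Optional titration days for subjects below therapeutic levels will not be counted towards the 365 day study period". The schedule in Appendix A marks AE assessment at screening, baseline and the titration visits as well as from Day 1 onward.

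Several groups can receive study drug before Day 1. Naïve subjects (3.1) and subjects weaned off intrathecal drugs (9.3) start low and titrate. For another group, 3.1 says: "For subjects using 1:12 conversion ratio, due to safety considerations, the conversion will be followed by up to five (5) optional titration days". Former control-arm subjects from CNS-HYD201US "will be titrated back to a therapeutic dose using one or more optional titration days prior to Day 1 of this study".

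SAP 9.5.1 counts treatment-emergent AEs from the first treatment with study drug, which it places at Baseline. It also reports subjects with any AE and lists all AEs, flagging those that are not treatment-emergent.

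**The concern.** A titrating subject is on study drug before Day 1. Read literally, 13.1 does not open the AE window until that time is over. These are a subject's first days on study drug. For 1:12 converters, the protocol itself gives safety as the reason for titrating.

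These subjects are in the Safety Population from any dose (SAP 6). If a site followed 13.1 rather than 5.1 or 13.2.1, early on-drug events would be missing from the numerator while the subject stayed in the denominator. Different sites could also apply different windows, and a reader of the report could not tell which window the primary safety data reflect.

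**Working it through.** **1. The windows side by side**

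| Source | Start | End | Covers on-drug titration? |
|---|---|---|---|
| Protocol 5.1 | Study drug administration | Final visit | Yes, by name |
| Protocol 13.1 | Study drug on Day 1 | Study medication stopped | No |
| Protocol 13.2.1 | Informed consent | A follow-up telephone call | Yes |
| Appendix A schedule | Screening | Final visit | Yes |

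**2. Can Day 1 in 13.1 mean the first dosing day?** No. Footnote a ties Day 1 to a therapeutic dose. Section 5.1 lists titration separately from Study Day 1. Footnote b treats the two as alternatives: "Initiation of Dosing (ie, Optional Titration Day or Day 1) visits may be combined".

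**3. The end points.** Those of 5.1 and 13.1 mostly coincide, because residual drug is removed at the final visit (9.5) and early stoppers have final-visit procedures (11.0). The call in 13.2.1 is not scheduled in Appendix A. The only telephone contact with subjects that the protocol describes is 24 hours after starting study drug (3.1), which cannot sensibly close the AE window.

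**4. Length of the omitted time.** The plan states no figure to reproduce. Inputs from Protocol 3.1 are up to five titration days, 3 to 14 days apart; the follow-up period is 365 days. Assume study drug starts on the first titration day, as footnote b allows. With k titration days there are k − 1 intervals from the first to the last, and k intervals if Day 1 falls one interval after the last. The documents do not state that final gap, so the second case is an assumption.

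| Titration days (k) | First to last, days | To Day 1 one interval later, days |
|---|---|---|
| 1 | 0 | 3 to 14 |
| 2 | 3 to 14 | 6 to 28 |
| 3 | 6 to 28 | 9 to 42 |
| 4 | 9 to 42 | 12 to 56 |
| 5 | 12 to 56 | 15 to 70 |

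Share of on-drug time for a subject who then completes 365 days = d / (d + 365):

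- k = 1, one interval: 3/368 = 0.8% to 14/379 = 3.7%.
- k = 5, first to last: 12/377 = 3.2% to 56/421 = 13.3%.
- k = 5, with one more interval: 15/380 = 3.9% to 70/435 = 16.1%.

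For a subject who stops during titration, all on-drug time falls before Day 1. For a subject who starts on Day 1 without titration, none does.

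**5. Who titrates?** The documents give no subgroup sizes and do not agree on the groups. Section 3.1 requires 1:6 converters to start on Day 1 without titration. Section 9.3 says that subjects on other intrathecal opioids may need titration days, and footnote c provides titration days for subjects switching from other opioids. These passages must be reconciled before the affected group can be defined.

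**The case against.** The strongest reply is that 13.1 is one stray sentence. Section 13.2.1 requires every AE from consent to be recorded in the source and the eCRF, 5.1 names the titration days, the schedule has AE assessment at those visits, and the eCRFs are fully source-verified. A site could drop titration events only by ignoring three other instructions. Besides, a titrating subject's first administration is not on Day 1, so 13.1 hardly has a literal application to that subject.

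Most of this stands, and it limits the consequence. It does not repair the text: for a titrating subject, 13.1 either omits the on-drug time or gives no usable start. Source verification shows that the eCRF matches the source; it does not show that sites asked about AEs over the same window.

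Three stronger readings are tempting, and the documents do not support them.

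- **That AEs were lost, or that the percentages above measure missed events.** They are shares of on-drug time for one hypothetical subject. No document shows a site applying 13.1 literally.
- **That the SAP excludes titration events.** The mention of Baseline in 9.5.1 is loose, but the missing-date sentence there refers to the first study drug treatment, and Protocol 9.2 puts baseline before study drug. First dose is the natural reading. Nor can it be said that the CSR would hide the matter: no CSR is among the documents, and full AE listings are planned.
- **That the gap reaches 84 days (6 × 14; 84/449 = 18.7%).** This adds a separate conversion dose one interval before the first titration day, on top of the assumed gap to Day 1. Neither interval is stated.

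**Conclusion.** The contradiction is plain in the text and concerns the primary endpoint. Section 13.1 is wrong as written and should be corrected.

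The consequence is limited: possible uneven capture of early on-drug AEs, confined to subjects who titrate before Day 1. With all five titration days the exposed period is 12 to 56 days, or 15 to 70 days on the assumption that Day 1 comes one interval later. The effect on AE incidence cannot be estimated, because neither the number of titrating subjects nor the practice at sites is known. Confidence is high in the contradiction and low in any actual loss of data.

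**What to change.** 1. **Protocol 13.1.** Align it with 5.1, 13.2.1 and the schedule, so that the AE window covers all time from first study drug in CNS-HYD202US, optional titration days included. Record AEs between consent and first dose as not treatment-emergent. Subjects rolling over from CNS-HYD201US may consent up to 30 days ahead (9.1; footnote e), so their events before transition should stay in that trial's record. Settle on one end point, and define or remove the unscheduled call in 13.2.1. Reconcile 3.1 with 9.3 and footnote c on titration in 1:6 converters. All subjects have completed, so this corrects the record and cannot change what was collected.
2. **SAP 9.5.1.** Replace the reference to first treatment at Baseline with the date of first study drug in CNS-HYD202US, whether an optional titration day or Day 1. Apply it to the locked data; onset dates (Protocol 5.1) and dose records (SAP 9.3) are already collected.
3. **CSR.** State that the protocol sections differed. Report how many subjects titrated and their recorded AEs with onset between first study drug and Day 1.

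The cost is one SAP phrase, one small extra summary and a short disclosure, with no new data or cleaning. If AEs are already counted from first dose, the counts do not change. SAP 8.4 suggests that some safety output may predate the current SAP version; if so, its AE start date needs to be confirmed.
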